2.2 Overview of Nonclinical Studies

AK002 is a humanized non-fucosylated immunoglobulin G1 (IgG1) monoclonal antibody directed against the inhibitory receptor Siglec-8, a member of the CD33-related family of Siglecs.

Siglec-8 has a restricted tissue distribution, expressed selectively on the surface of mature eosinophils and mast cells, but not in early precursors of these cell populations. In blood, binding of AK002 to Siglec-8 induces ADCC against eosinophils, leading to rapid and sustained depletion of these cells from circulation. In the tissue, AK002 induces direct apoptosis of eosinophils and inhibition of mast cells. This profile of activity may provide clinical benefit in diseases in which these cell types play a role, such as eosinophilic gastritis and eosinophilic duodenitis.

Siglec-8 is not expressed in species other than humans, and therefore 2 novel mouse models have been developed for *in vivo* testing of AK002. AK002 has been studied in Siglec-8 humanized and transgenic mouse models and with human blood and tissue cells. The first model uses immunodeficient mice capable of generating human immune cells including mast cells and eosinophils when engrafted with human hematopoietic stem cells. The ability of anti-Siglec-8 antibodies to inhibit mast cell-mediated reactions has been evaluated in this model. The second rodent model is a transgenic mouse line that expresses human Siglec-8. The expression of Siglec-8 on the cell surface in these mice is restricted to eosinophils, mast cells, and basophils, a pattern of surface expression equivalent to that in humans. Anti-Siglec-8 antibodies can prevent immunoglobulin E (IgE)-mediated anaphylaxis in this transgenic mouse line, indicating that Siglec-8 is pharmacologically active in the model. The ability of AK002 to affect mast cells and eosinophils has been evaluated in this model.

AK002 inhibits IgE-mediated mast cell degranulation and release of the newly formed mediator prostaglandin D2 in vitro without affecting mast cell viability. In peripheral blood preparations from normal human donors, AK002 shows selective depletion of eosinophils. Importantly, in a whole-blood cytokine-release assay using immobilized AK002 to enhance the potential for antibody crosslinking, AK002 did not lead to dose-dependent release of pro-inflammatory cytokines.

To evaluate the in vivo activity of anti-Siglec-8 antibodies in an immunocompetent rodent model, a transgenic mouse strain has been developed that selectively expresses human Siglec-8 on the surface of mouse mast cells, eosinophils, and basophils. In single- and repeat-dose studies in Siglec-8 transgenic mice, AK002 demonstrated selective depletion of peritoneal mast cells and circulating and tissue (spleen) eosinophils and basophils.

In 2 Good Laboratory Practice (GLP) toxicity and toxicokinetic studies, AK002 was well tolerated at doses of 50 mg/kg and 100 mg/kg, 5-fold and 10-fold, respectively, the level of the highest dose proposed to be studied in humans. AK002 showed sustained systemic exposure in Siglec-8 transgenic mice with an extended terminal half-life estimated as 272 hours or 337 hours following single intravenous administration of 50 mg/kg or 100 mg/kg, respectively, after 5 weekly doses at these dose levels. There was no evidence of anti-drug antibodies (ADA) in either study. Decreases in eosinophil counts in both sexes were observed, which reflect the expected pharmacology of AK002. The no-observed-adverse-effect-level following intravenous administration of AK002 to transgenic mice was 100 mg/kg, which supports the Phase 1 studies in humans.

2.3 Overview of Clinical Studies

AK002, administered as an intravenous infusion has been previously tested in healthy volunteers and in patients with indolent systemic mastocytosis (ISM), chronic urticaria (CU), severe allergic conjunctivitis (AC), mast cell gastritis, and eosinophilic gastritis (EG) and/or eosinophilic duodenitis (EoD), which was previously referred to as eosinophilic gastroenteritis (EGE) in previous versions of this protocol.

Multiple doses of 3 mg/kg AK002 have been given to patients with ISM, CU, severe AC, mast cell gastritis, and EG and/or EoD. In these studies, patients reported improvements in disease symptoms with AK002 pharmacodynamic (PD) activity being observed for prolonged periods of time and AK002 pharmacokinetic (PK) parameters demonstrating [REDACTED]
[REDACTED].

To date, over 300 healthy volunteers and patients with ISM, CU, severe AC, EG/EoD, EoE, and mast cell gastritis have been enrolled in clinical studies. In total, 65 EG/EoD patients were enrolled in the double-blind Study AK002-003 for which this protocol is the open-label extension.

In general, AK002 has been well tolerated. The most common treatment-emergent adverse events (TEAE) observed were infusion-related reactions (IRR). Most IRR were mild to moderate, and 2 IRR were classified as serious but resolved within 24 hours. Common symptoms of IRR were headache, nausea, sweating, flushing, and redness. Most IRR that occurred during the infusion could be managed by slowing or temporary interruption of the infusion, with minimal intervention. Transient lymphopenia was observed after infusion of AK002 but was not associated with any clinical consequence, and lymphocytes recovered within 24 hours. A sustained depletion of eosinophils was observed that is consistent with the mechanism of action of AK002. In 6 healthy volunteers who received 2 doses of 0.3 mg/kg, 4 weeks apart, the second dose was better tolerated than the first dose. This was also the case in patients with ISM, CU, severe AC, and EG/EoD, with fewer adverse events (AE) reported during the second and subsequent infusions when compared to the first infusion.

In the randomized, double-blind, placebo-controlled Phase 2 study of AK002 in 65 patients with EG and/or EoD, patients were randomized to receive monthly doses of placebo, low dose AK002 (0.3, 1, 1, and 1 mg/kg), or high dose AK002 (0.3, 1, 3, and 3 mg/kg) in a 1:1:1 ratio (Dellon, 2020). All primary and secondary endpoints were met in the study. There was a 97% and 92% mean reduction in eosinophils in the stomach/duodenum at the high dose and low dose, respectively, versus 10% increase on placebo ($p<0.0001$).

The reduction of eosinophils was associated with a statistically significant reduction in total symptom score (TSS) on 8 symptom intensity scores (TSS8) of 58% in the high dose group and 49% in the low dose group versus 24% reduction in the placebo group ($p=0.0012$ and $p=0.015$, respectively). Improvement in symptoms was observed within 24 hours of the first dose of study drug. In addition, 70% of high dose treated patients and 68% of low dose treated patients were treatment responders (defined as $>30\%$ improvement in TSS and $>75\%$ reduction from baseline in tissue eosinophils) versus 5% for placebo treated patients ($p<0.0001$).

When patients complete Study AK002-003 or are discontinued from treatment due to high eosinophil counts prior to infusions 2, 3, or 4, they are eligible to enter this open-label extension study, AK002-003X.

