Patients will receive up to 26 monthly intravenous infusions of AK002 in an open-label manner. The first infusion of AK002 will be 1 mg/kg, and subsequent infusions will be 3 mg/kg.

If a monthly infusion of AK002 is missed the patient will be permitted to make up the missed dose after the 26th month so that all patients have the chance to receive a total of 26 infusions.

An EGD with biopsy will occur on Day 211 (± 3), Day 547 (± 3), and Day 729 (± 3) or 28 (± 3) days after the last dose of study drug, if early termination (ET) or if patient received additional missed doses.

Patients will be followed for 84 (± 3) days after the last dose of study drug. Follow-up visits will occur on Extension Day 736 (± 3), Day 757 (± 3), and Day 785 (± 3) or 35 (± 3), 56 (± 3), and 84 (± 3) days after last dose of study drug, if ET or if patient received additional missed doses.

Total duration of Study AK002-003X will be approximately 28 months if doses are administered monthly and none are missed, or longer, as needed for the patient to receive all 26 doses.

Approximately 60 patients will be enrolled in Study AK002-003X, based on enrollment of Study AK002-003.

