6.3 Efficacy Endpoints

Daily self-administration of a disease-specific patient questionnaire (PRO Questionnaire) will be used to evaluate signs and symptoms associated with EG and/or EoD. Changes in quality of life will be measured by the Short-Form 36 Health Survey (SF-36) questionnaire. Changes in the number of eosinophils in gastric and/or duodenal mucosa from baseline will also be evaluated.

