11.2.5 Esophago-Gastro-Duodenoscopy with Biopsy

An EGD with biopsy will be performed on Day 211 (± 3), Day 547 (± 3), and Day 729 (± 3) or 28 (± 3) days after last dose of study drug, if ET. Biopsy samples will be collected according to standardized instructions and will be sent to the Central Lab designee for fixing and staining. A Central reader will report, among other things, maximum number of eosinophils per hpf, maximum number of tryptase-positive mast cells per hpf, and gastric biopsies will be graded using the Sydney System on inflammation, metaplasia, atrophy, and reactive gastropathy. The Marsh Scale Classification will be used to grade duodenal samples. The baseline EGD from Study AK002-003 will be used for comparison.

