15.6 Pharmacodynamic/Efficacy-Related Analyses

The change from baseline to end of study in the SF-36 total and domain scores will be summarized descriptively. Change and percent change from baseline to each scheduled study visit in blood eosinophil count will be summarized descriptively.

Data from the ePRO and SF-36 from Extension Day 562 through end of study may be analyzed according to analysis plans independent of the EDC database and Statistical Analysis Plan for AK002-003X.

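### Section 11.2.5 compares extension biopsies only with the untreated AK002-003 baseline, with no split by AK002-003 arm, which mutes any later loss of tissue effect in former AK002 patients

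*Combined protocol and SAP*

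**What the plan says.** Section 5.1 sets the biopsy times: "An EGD with biopsy will occur on Day 211 (± 3), Day 547 (± 3), and Day 729 (± 3"), with the last one moved to 28 days after the final dose for early termination or made-up doses. Table 1 schedules no EGD at extension entry.

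Section 11.2.5 gives the reference for these biopsies: "The baseline EGD from Study AK002-003 will be used for comparison". Section 6.3 lists the endpoint without defining its baseline: "Changes in the number of eosinophils in gastric and/or duodenal mucosa from baseline will also be evaluated".

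Section 15.6 covers SF-36 and blood counts. For blood it says: "Change and percent change from baseline to each scheduled study visit in blood eosinophil count will be summarized descriptively". It specifies no summary of tissue eosinophils and no analysis by AK002-003 arm. Section 15 leaves full detail to a separate SAP, whose text is not in the document reviewed.

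Section 2.3 reports the tissue result of AK002-003: "There was a 97% and 92% mean reduction in eosinophils in the stomach/duodenum at the high dose and low dose, respectively". For the placebo arm it gives a rise of 10%. Biopsy results after treatment began therefore exist for all three arms.

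**The concern.** The objective in Section 4 is longer-term follow-up of safety and efficacy, together with access to AK002 for former placebo patients. For tissue, that poses two questions. In patients already treated with AK002, does the effect last? In former placebo patients, does it appear?

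A single untreated reference suits the second question. It suits the first poorly, because most of the change from that reference was reached before Extension Day 1. A pooled figure with no split by arm also mixes the two groups. The protocol is not uniform on this either: Section 11.2.1 takes the Day 113 visit of AK002-003, which is extension entry for completers, as the SF-36 baseline.

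At stake is whether the biopsy results can be read as evidence of durability. The study makes no formal inference, so the choice of reference largely determines what the summary says.

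**Working it through.** **Inputs**
- Tissue eosinophil change in AK002-003 (Section 2.3): −97% high dose, −92% low dose, +10% placebo.
- Allocation in AK002-003 (Section 2.3): "or high dose AK002 (0.3, 1, 3, and 3 mg/kg) in a 1:1:1 ratio".
- Extension size (Section 5.1): "Approximately 60 patients will be enrolled in Study AK002-003X, based on enrollment of Study AK002-003".
- Tissue cut-off in AK002-003 (Section 2.3): more than 75% reduction, one component of a composite responder definition that also requires more than 30% symptom improvement.

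The 97% and 92% are observed results given without counts, standard deviations or arm sizes, so they cannot be recomputed. The steps below are illustrative. They apply each arm's mean percent change to every patient as a common ratio.

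**Step 1. Residual count at the end of AK002-003, as a fraction of baseline**
- High dose: 1 − 0.97 = 0.03
- Low dose: 1 − 0.92 = 0.08
- Placebo: 1 + 0.10 = 1.10

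**Step 2. What an m-fold rise since then looks like on the planned reference**

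Apparent reduction = 1 − m × residual.

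| Rise since end of AK002-003 | High dose | Low dose |
|---|---|---|
| none (m = 1) | 97% | 92% |
| doubling (m = 2) | 1 − 0.06 = 94% | 1 − 0.16 = 84% |
| tripling (m = 3) | 1 − 0.09 = 91% | 1 − 0.24 = 76% |

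Counts reach the 75% cut-off only after a rise of 0.25/0.03 = 8.3-fold (high dose) or 0.25/0.08 = 3.1-fold (low dose). A full return to baseline, 1/0.03 = 33-fold or 1/0.08 = 12.5-fold, would read as 0% reduction.

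**Step 3. Pooled reduction already present before any extension dose**

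Pooled reduction = 1 − weighted mean of the residuals.
- Equal rollover of the three arms (assumption; 60 × 2/3 = 40 former AK002 patients): 1 − (1.10 + 0.08 + 0.03)/3 = 59.7%.
- Former placebo 25%, the rest split equally: 1 − (0.25 × 1.10 + 0.375 × 0.08 + 0.375 × 0.03) = 68%.
- Former placebo 40%, the rest split equally: 1 − (0.40 × 1.10 + 0.30 × 0.08 + 0.30 × 0.03) = 53%.

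**Step 4. Pooled figure if former placebo patients reach a 97% reduction (equal rollover)**
- Former AK002 patients stable: 1 − (0.03 + 0.08 + 0.03)/3 = 95%.
- Former AK002 counts tripled: 1 − (0.03 + 0.24 + 0.09)/3 = 88%.

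A threefold rise in two thirds of the patients moves the pooled figure by about 7 percentage points.

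**Step 5. Former placebo patients**

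A fall to 10% of the AK002-003 baseline is 90.0% on the planned reference and 1 − 10/110 = 90.9% from the post-placebo count. On average the choice of reference hardly matters for this group.

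**The case against.** The untreated baseline is a legitimate reference. It measures total effect, it is common to all three former arms, and it serves patients discontinued for high eosinophil counts, who may have no later AK002-003 biopsy. This stands, and it is why the baseline should be kept.

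A reader might infer that loss of effect would be hidden. The documents do not support that. A drop from 97% to 91%, or from 92% to 76%, is visible beside the AK002-003 result. Three extension EGDs allow a time trend, and Section 15 has all patient data listed. The signal is muted, not lost. Listings and a trend still do not replace a summary aimed at durability.

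A reader might also infer that the sponsor plans no other comparison. That cannot be asserted: Section 11.2.5 is a procedures section, it does not exclude other references, and the separate SAP may add them.

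The fold rises are scenarios, and a ratio taken from about 3% of baseline makes small absolute differences look large. That is fair. It is also the reason to report the second comparison in absolute counts. Finally, the study is descriptive and no decision rule depends on this reference, so the point concerns interpretability and not the validity of a test.

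**Conclusion.** The point holds for the protocol text. The only biopsy comparator it names carries the AK002-003 reductions of 97% and 92% into the extension result, and Section 15.6 offers neither a tissue summary nor a split by AK002-003 arm. Durability in former AK002 patients is therefore answered poorly: on the illustration, a threefold rise still reads as a 91% or 76% reduction, and a pooled reduction of about 60% (53% to 68% over the rollover mixes shown) predates the first extension dose.

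These sizes rest on treating arm means as common ratios and on assumed rollover by arm. The timing of the later AK002-003 EGD is not given, and the 92–97% may not apply to patients discontinued early for high eosinophil counts.

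It would be tempting to add that the reference also distorts the effect of first AK002 exposure in former placebo patients. The documents' own figures do not support this: the average shift is under one percentage point.

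**What to change.** Keep the AK002-003 baseline EGD as the measure of total effect, and amend Sections 11.2.5 and 15.6 as follows.

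- Summarise tissue eosinophils at Days 211, 547 and 729 (or the early-termination EGD) by AK002-003 arm: placebo, low dose, high dose.
- Add each patient's last AK002-003 EGD as a second, durability reference, and show absolute counts and absolute change against it. Do not use percent change here, because it is unstable near zero and undefined at zero.
- Where a patient has no later AK002-003 EGD, report against baseline only and state how many such patients there are.
- Optionally, report how many patients with more than 75% tissue reduction at the end of AK002-003 keep it at each extension EGD, with a note that this is only the tissue part of that study's composite responder definition.

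If the separate SAP already contains this, aligning the protocol wording is enough. The cost is a wording change and one extra table. No new procedure is needed: the same sponsor holds the AK002-003 counts, and Section 10.1 keeps the same patient number. The durability figures may look less favourable than change from the untreated baseline.

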2.4 Eosinophilic Gastrointestinal Disorders

Eosinophilic gastrointestinal disorders (EGID) are chronic inflammatory disorders characterized by infiltration of eosinophils along different segments of the gastrointestinal tract, in the absence of any cause of the eosinophilia (Caldwell, 2014).

Eosinophilic gastritis and/or eosinophilic duodenitis represent what are believed to be rare types of EGID that are characterized by chronic, often severe inflammation due to patchy or diffuse infiltration of eosinophils into layers of the stomach, small intestine, or both (Prussin, 2014; Reed, 2015; Zhang, 2017).

The diagnosis is made based on clinical presentation (gastrointestinal symptoms) combined with increased tissue eosinophils in biopsy specimens from the stomach and/or small intestine without any other cause for the eosinophilia. Involvement of the small intestine is typically assessed by performing duodenal biopsies using an esophago-gastro-duodenoscopy (EGD) and has been referred to as EGE or eosinophilic enteritis, though EoD is more accurate.

The gastrointestinal symptoms are believed to be due to the release of inflammatory mediators from activated eosinophils, and likely mast cells. Symptoms that are often severe and debilitating commonly include abdominal pain, nausea, bloating, early satiety, loss of appetite, abdominal cramping, vomiting, diarrhea, and weight loss (Alhmoud, 2016; Lopez-Medina, 2015; Mansoor, 2017; Reed, 2015). Jensen (2016) estimated the prevalence of EG and EoD to be 6.3/100,000 and 8.4/100,000, respectively (for patients from 1 to 64 years of age). Mansoor (2017) estimated the overall prevalence of EG to be 5.1/100,000 persons.

Patients may also have concomitant atopic diseases like food allergy, asthma, and atopic dermatitis, which further impacts quality of life and contributes to health care costs. Additionally, 8% to 10% of patients have concomitant EoE (Jensen, 2016).

There are no FDA-approved treatments for EG and/or EoD. Current therapies and disease management includes dietary restriction/elimination, proton pump inhibitors (PPI), antihistamines, systemic or swallowed corticosteroids, and occasional off-label use of immunomodulatory biologics (Prussin, 2014; Reed, 2015; Zhang, 2017).

Proton pump inhibitors have little to no benefit in patients with EG or EoD, despite reports of providing partial benefit in some patients with EoE (Katz, 2013). Restricted/elemental diets are not effective long-term treatment as they require strict compliance and, in the case of elemental diets, are expensive and often not reimbursed by insurance. In addition, compliance is very poor and patient quality of life is greatly impacted (Bedell, 2018; Peterson, 2013; Wechsler, 2014).

Corticosteroids, systemic or swallowed, have been shown to provide symptom relief but are not appropriate for long-term treatment due to numerous side effects and associated risks including adrenal insufficiency, bone demineralization, increased chance of infection, osteoporosis, behavioral issues, and weight gain.

By reducing the number of blood and tissue eosinophils and inhibiting the activation of mast cells, AK002 may be useful in the treatment of patients with EG and/or EoD. This premise is supported by the Phase 2 data with AK002 that shows significant improvements in histology and symptoms in these patients.

Given there are no approved therapies for these chronic and debilitating diseases, better treatment options are clearly needed to manage EG and EoD.

3. Rationale for Study and Dose Selection

Based on experience with AK002 in healthy volunteers and in patients with ISM, CU, severe AC, mast cell gastritis, and EG/EoD, the proposed AK002 dose regimen is up to 26 monthly intravenous infusions of AK002.

In the randomized, double-blind, placebo-controlled Phase 2 study of AK002 in 65 patients with EG and/or EoD, 2 dose levels were evaluated: a lower dose regimen (4 monthly doses of AK002 at 0.3, 1, 1, and 1 mg/kg) and a higher dose regimen (4 monthly doses of AK002 at 0.3, 1, 3, and 3 mg/kg). [REDACTED]

[REDACTED]

[REDACTED]

A starting dose of 1 mg/kg AK002 followed by a dose of 3 mg/kg AK002 for the subsequent infusions has been chosen for the Phase 2 extension study with AK002 in patients with EG and/or EoD.

4. Study Objective

The objective of the study is to generate open-label, longer-term safety, tolerability, and efficacy follow-up data in patients with EG and/or EoD who completed Study AK002-003 or were discontinued from treatment due to high eosinophil counts prior to infusions 2, 3, or 4.

The objective of this extension study is also to give patients that received placebo in Study AK002-003 access to AK002.

5. Study Design

5.1 Study Overview

This is a Phase 2, multicenter, open-label, extension study to evaluate the safety, tolerability, and efficacy of AK002 in patients with EG and/or EoD. Patients who complete Study AK002-003 will have the option to receive AK002 in an open-label manner. A patient will be categorized as having completed Study AK002-003 if 4 infusions of study drug are administered and the patient is followed through Day 113 (± 3 days).

Patients who were discontinued from treatment in Study AK002-003 at the recommendation of the unblinded safety monitor for high eosinophil counts prior to infusions 2, 3, or 4, will have the option to receive AK002 in an open-label manner.

Patients who enroll in Study AK002-003X will receive monthly AK002 infusions for a maximum of 26 intravenous doses. During Extension Study AK002-003X, patients will maintain the same patient number that was assigned in Study AK002-003.

Safety will be assessed by body weight, vital signs, symptom-directed physical examination, complete blood count (CBC) with differential, blood chemistry, urinalysis, and assessment of AE (including adverse events of special interest [AESI] and serious adverse events [SAE]). In addition, blood samples will be obtained for evaluation of anti-drug antibodies (ADA).

This extension study does not include fasting requirements. Patients underwent a standardized baseline evaluation of eating habits, food habits/restrictions, and food avoidance behaviors during Study AK002-003 and will be asked at study visits whether any changes have been made from the baseline diet.

Patients completing Study AK002-003 and wanting to enter the extension study will begin extended dosing on or about Day 113 of Study AK002-003 (following final assessments of Study AK002-003), which will be considered Day 1 of Study AK002-003X. If patients cannot start extended dosing within 45 days of AK002-003 Day 113, current baseline safety assessments must be completed prior to Day 1 of Study AK002-003X. Patients discontinued from treatment in Study AK002-003 due to high eosinophil counts prior to infusions 2, 3, or 4 may begin extended dosing within 6 months of the last dose in Study AK002-003.

Patients discontinued from the AK002-003 study for high eosinophil counts and patients that completed AK002-003 but were not enrolled into AK002-003X within 45 days of Day 113 will require current safety evaluations.

Patients will receive up to 26 monthly intravenous infusions of AK002 in an open-label manner. The first infusion of AK002 will be 1 mg/kg, and subsequent infusions will be 3 mg/kg.

If a monthly infusion of AK002 is missed the patient will be permitted to make up the missed dose after the 26th month so that all patients have the chance to receive a total of 26 infusions.

An EGD with biopsy will occur on Day 211 (± 3), Day 547 (± 3), and Day 729 (± 3) or 28 (± 3) days after the last dose of study drug, if early termination (ET) or if patient received additional missed doses.

Patients will be followed for 84 (± 3) days after the last dose of study drug. Follow-up visits will occur on Extension Day 736 (± 3), Day 757 (± 3), and Day 785 (± 3) or 35 (± 3), 56 (± 3), and 84 (± 3) days after last dose of study drug, if ET or if patient received additional missed doses.

Total duration of Study AK002-003X will be approximately 28 months if doses are administered monthly and none are missed, or longer, as needed for the patient to receive all 26 doses.

Approximately 60 patients will be enrolled in Study AK002-003X, based on enrollment of Study AK002-003.

